2 INTRODUCTION: BACKGROUND INFORMATION AND SCIENTIFIC RATIONALE

This study will be conducted in compliance with the protocol, International Conference on Harmonization (ICH), Good Clinical Practice (GCP) guidelines and applicable regulatory requirements.

2.1 Background Information

Punctal plugs are medical devices designed to block the drainage of tear fluid from the eye; several models are approved and commercially available. Punctal plugs are classified by the FDA as a Class II Pre-Amendment medical device. Furthermore, plugs are not identified as significant risk devices on the FDA Information Sheet titled “Significant Risk and Non-Significant Risk Medical Device Studies.”

Mati Therapeutics Inc. is the first to use punctal plugs as an anchoring device for a drug delivery platform. A drug-eluting core is inserted into Mati’s proprietary punctal plug (Evolute® PPDS), which allows medication to be continuously released into the tear film of the eye over a period of time. This platform has the potential to become a viable alternative to eye drop therapy and could address significant compliance issues that currently exist with patients who will not or cannot properly self-administer eye drop medications.

Cataract surgery is the most commonly performed surgery in the nation, with more than 3.5 million of these procedures done annually in the United States. Multiple studies have reported noncompliance and self-administration difficulties with topical medications among cataract surgery patients ([Kholdebarin 2008](#); [Winfield 1990](#)). A 2014 study showed that 92.6% of patients incorrectly administered topical medications after cataract surgery ([An 2014](#)).

Although recent advances in cataract extraction (CE) surgery have decreased the physical trauma associated with ocular surgery, disruption of the blood–aqueous barrier during surgery can lead to the release of inflammatory mediators, increasing the risk of secondary ocular complications. Favorable post-operative outcome depends on the proper use of topical medications to shorten the inflammatory response induced by cataract surgery. Untreated, post-operative inflammation can increase the risk of mild iritis with increased cells and flare in the anterior chamber (AC) and can interfere with the patient’s visual rehabilitation. In rare cases, inflammation can lead to complications such as cystoid macular edema, posterior capsule fibrosis, keratopathy, fibrin reaction, or chronic uveitis. Therefore, anti-inflammatory agents are routinely prescribed to resolve post-op signs and symptoms of cataract surgery more rapidly and to improve patient comfort.

The US Food and Drug Administration approved Nepafenac ophthalmic suspension 0.1% (NEVANAC®) in 2005 and Nepafenac ophthalmic suspension 0.3% (ILVERO®) in 2005 from Alcon Laboratories, Fort Worth, Texas, USA. Both ophthalmic suspension concentrations received an indication for the treatment of pain and inflammation associated with cataract surgery.

NEVANAC® ophthalmic suspension was compared with its vehicle in two double-masked, randomized clinical trials in which patients were dosed three-times-daily beginning one day prior to cataract surgery, continued on the day of surgery and for the first two weeks of the postoperative period. Nepafenac 0.1% treated patients were less likely to have ocular pain and measurable signs of inflammation (cells and flare) in the early postoperative period through the end of treatment than those treated with its vehicle. For ocular pain, both studies had a significantly higher percentage of patients (approximately 80%) in the Nepafenac group reporting no ocular pain on the day following cataract surgery (Day 1) compared to those in the vehicle group (approximately 50%).

ILEVRO® ophthalmic suspension was compared with its vehicle in two double-masked, randomized clinical trials in which patients were dosed once a day beginning one day prior to cataract surgery, continued on the day of surgery and for the first two weeks of the postoperative period. Nepafenac 0.3% treated patients were less likely to have ocular pain and measurable signs of inflammation (aqueous cells and flare) in the early postoperative period through to the end of treatment than those treated with its vehicle. In the two studies, Nepafenac cleared inflammation at day 14 post operation in 65% and 61% of patients compared to 32% and 24% of patients on vehicle. Pain free rates in the Nepafenac group were 86% and 84% compared to 46% and 38% of patients on vehicle. The Day 14 results for reduction of both pain and inflammation were statistically significantly superior to the vehicle.

This study will enroll approximately 75 qualified subjects (75 eyes) who have given written consent, have met all study inclusion/exclusion criteria and are scheduled to undergo unilateral cataract surgery with the implantation of an intraocular lens (IOL) will be enrolled in to the study.

2.2 Rationale

Past clinical studies with topical dosing of 0.1% and 0.3% ophthalmic suspensions of Nepafenac (NEVANAC®/ILEVRO®) have demonstrated the safety and efficacy of Nepafenac in the treatment of pain and inflammation associated with ocular surgery. The objective for this study is to evaluate the use of a punctal plug drug delivery device that can deliver a sustained, safe and effective concentration of Nepafenac to a subject undergoing cataract surgery, for the treatment of post-operative ocular pain and inflammation.

Placebo has been selected as the control group. This will allow the results obtained from this study to be compared to treatment results from similarly design Phase 3 and 3B studies of Nepafenac.

2.3 Potential Risks and Benefits

2.3.1 Known Potential Risks

A study subject randomized to receive N-PPDS may have unforeseen risk and could exhibit moderate to severe post-op inflammation and/or ocular pain. However, the risk associated with using N-PPDS to deliver a sustain release of Nepafenac are anticipated to be similar, if not less than, those of commercially available topical 0.1% and 0.3% ophthalmic suspension

of Nepafenac and silicone punctal plug products. In ocular surgery clinical studies with Nevanac®, adverse reactions that occurred in 5-15% of study patients included capsular opacity, decreased visual acuity, foreign body sensation, increase intraocular pressure, and sticky sensation. Adverse reactions that occurred in 1-5% of study patients included conjunctival edema, corneal edema, dry eye, lid margin crusting, ocular discomfort, ocular hyperemia, ocular pain, ocular pruritus, photophobia, tearing and vitreous detachment. Some of these reactions may have been the consequence of the surgical procedure. A summary of known potential risks to humans of topical 0.1% and 0.3% ophthalmic suspension of Nepafenac can be found in the NEVANAC® and ILEVRO® prescribing information (see [Appendices 4 and 5](#)).

A study subject randomized to receive a placebo Punctal Plug Delivery System (p-PPDS) could exhibit moderate to severe post-op inflammation and/or ocular pain. Other risks associated with using a p-PPDS are anticipated to be similar to commercially available punctal plugs use in humans. A study subject could experience ocular discomfort, epiphora, loss of plug, ocular inflammation, and subconjunctival hemorrhage. Less common, but serious, side effects are pyogenic granuloma, damage to the muscle at the opening of the punctum, canaliculitis, or migration of the plug into the canaliculus requiring irrigation or surgery.

2.3.2 Known Potential Benefits

The potential benefit associated with the use of N-PPDS to deliver a sustain release of nepafenac is the reduction of post-operative ocular inflammation and ocular pain. In addition, the use of N-PPDS eliminates the subject non-compliance issue with daily dosing of an anti-inflammatory drug.

A summary of known benefits to humans of topical 0.1% and 0.3% ophthalmic suspensions of nepafenac can be found in the NEVANAC® and ILEVRO® prescribing information (see [Appendices 4 and 5](#)).

3 OBJECTIVES AND PURPOSE

To evaluate the safety and efficacy of N-PPDS in the treatment of post-operative ocular pain and inflammation associated with cataract surgery.

4 STUDY DESIGN AND ENDPOINTS

4.1 Description of the Study Design

This is a Phase 2, multi-center, randomized, parallel-arm, double-masked, placebo-controlled study. One (1) to 2 days prior to their scheduled cataract surgery, each study subject will be randomized (2:1) in to one of two treatment groups:

Group A: A total of 50 study subjects (50 eyes) will have an N-PPDS inserted in the lower punctum of their scheduled surgical eye.

Group B: A total of 25 study subjects (25 eyes) will have a p-PPDS inserted in the lower punctum of their scheduled surgical eye.

All plugs will remain in the study subject's lower punctum for a period of 2 weeks following cataract surgery.

4.2 Study Endpoints

The study will be complete when 75 study subjects (75 eyes) have been evaluated at Visit 7 (Day 14 post-op) or have been terminated from the study.

4.2.1 Primary Efficacy Endpoint

The primary effectiveness endpoint will analyze the Investigator's evaluation of study subject's ocular pain following cataract surgery compared with placebo at 1, 3, 7 and 14 days post-op.

4.2.2 Secondary Efficacy Endpoints

The secondary effectiveness will analyze the complete (CR) and partial response (PR) to therapy regarding the Summed Ocular Inflammation Score (sum of the mean anterior chamber cells and flare) following cataract surgery compared with placebo at 3, 7 and 14 days post-op.

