- d. Record the use of permitted concomitant medication(s), alteration in use or addition of any open-label medication(s) during the study period.
- e. Investigator evaluation of ocular pain

NOTE: The Investigator that interviews and record the subject's response to ocular pain at Visit 4 (Day 1 post-op) should interview the subject at ALL post-op visits (Visits 4, 5, 6 and 7).

- f. Assessment of any reported Adverse Events

Additional procedures will be performed and recorded at Visit 1 (Screening/Baseline, Day -30 to -1), Visit 2 (Punctal Plug Insertion Visit, 1-2 days pre-op), Visit 3 (Surgical day, Day 0) and Visit 7 (Final study visit, Day 14 post-op)

- a. Visit 1:

- Grade Cataract Density (scale: 1 to 4)
- Fundus examination
- Evaluation of lower puncta

- b. Visit 2:

- Insertion of masked study punctal plug
- Inspection of the punctal plug via the slit-lamp in addition, performed at each follow-up visit.

NOTE: All NSAIDs or corticosteroid medications, with the exception of a subject who has been prescribed and has been taking a baby aspirin (≤ 81 mg/daily), must be discontinued at least 48 hours prior to the insertion of the punctal plug.

- c. Visit 3:
 - Pupil measurements (prior to and immediately following surgery)
 - Monocular cataract extraction/IOL implantation
 - Indicate the incision Type, Location and Size (mm)
 - Nucleus removal time
 - Ease Cortex removal
 - Effective Phaco Power (Phaco Time and Power)
 - Type of IOL (e.g., monofocal, toric etc.) and lens power
 - Record any surgical complications
 - Subject reported AEs prior to or after surgery
- d. Visit 7:
 - Fundus examination

Study Efficacy Variables:

Primary: Investigator evaluation of study subject post-op ocular pain at visits 4, 5, 6 and 7.

Secondary: Mean anterior chamber scores for cells and flare at visits 4, 5, 6 and 7

Study Safety Variables: Safety outcome measures include

- a. Distance visual acuity
- b. Slit Lamp Examination (Lid, conjunctiva, cornea)
- c. Fundus Examination
- d. Use of concomitant (rescue) medication(s)
- e. Incidents of reported Adverse Events

Sample Size Determination: Since this is a pilot study, no formal sample size estimation was performed.

Schedule of Assessments, Events

EXAM PARAMETERS	v1	v2	v3	v4	v5	v6	v7
Inform Consent/HIPPA	1						
Demographic data/Medical Hx	1 A						
Concomitant Medication	1	2	3	4	5	6	7
Urine Pregnancy Test (if applicable)	1 B						
Subject Randomization to Treatment		2					

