Investigator Evaluation of Ocular Pain	1 C	2		4 F	5 F	6 F	7 F
Uncorrected Distance VA	1 C				5	6	7
Manifest Refraction	1 C					6	7
Best-Corrected Distance VA	1 C					6	7
Slit Lamp Examination	1 C			4 F	5 F	6 F	7 F
Insertion of Masked Punctal Plug		2					
Inspection of Masked Punctal Plug		2 D	3 E	4 D	5 D	6 D	7 D
Evaluation of lower puncta	1						
Pupil Measurements			3 G				
Type and Grade Cataract	1						
Monocular Cataract Extraction/IOL Implantation			3				
Fundus Examination	1						7
Removal of Masked Punctal Plug							7 H
Adverse Event Recording		2	3	4	5	6	7

Keys to Abbreviations:

- A = Prior 12 months
- B = Pregnancy test (women of childbearing potential)
- C = Evaluation of Both Eyes
- D = Evaluation using slit-lamp
- E = Visual inspection after surgery
- F = Investigator that performs the slit-lamp and/or ocular pain evaluation
at Visit 4 (Day 1 post-op) should perform ALL post-op visit evaluations
- G = Measurement to occur prior to surgery and immediately after surgery
- H = All masked punctal plugs must be removed at the subject last visit

Visit Schedule:

- v1 = Day -30 to -1
- v2 = 1 to 2 days prior to surgery
- v3 = Surgery Day
- v4 = 1 day post-op
- v5 = 3 ± 1 days post-op
- v6 = 7 ± 1 days post-op
- v7 = 14 ± 2 days post-op

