5.2 Subject Pre-Operative Exclusion Criteria

The following are pre-surgical exclusion criteria for a prospective study subject:

1. A subject with a history of complications, adverse events, trauma or disease in the nasolacrimal area, whether or not it was due to punctal plug wear, including but not limited to dacryocystitis, inflammation or canaliculitis in either eye
2. A subject with structural lid abnormalities (e.g., ectropion, entropion) in their scheduled surgical eye
3. A subject with a puncta >0.9 mm prior to dilation in their scheduled surgical eye
4. A subject experiencing any ocular pain in either eye at the screening visit or on the day the plug is to be inserted
5. A subject with any moderate to severe lid, conjunctival or corneal findings in either eye at the screening visit
6. A subject with any signs of intraocular inflammation (cells/flare) in either eye at the screening visit
7. A subject with a known sensitivity to nepafenac or any inactive ingredient of the punctum plug, silicone, fluorescein, topical anesthetic, or any other products required for study procedures or cataract surgery
8. A subject with a history as a steroid responder

9. A subject with a known or suspected allergy or hypersensitivity to non-steroidal anti-inflammatory drugs (NSAIDs), or to any component of the test article
10. A subject with only one eye with potentially good vision
11. A subject with a known pathology that may affect visual acuity (as determined by the Investigator); particularly retinal changes that affect vision (macular degeneration, cystoid macular edema, proliferative diabetic retinopathy, etc.) in their scheduled surgical eye
12. A subject that has a condition associated with the fluctuation of hormones that could lead to refractive changes
13. A subject with amblyopia or strabismus
14. A subject with capsule or zonular abnormalities with preoperative lens tilt and/or decentration (e.g., Marfan's syndrome), or may affect postoperative centration or tilt of the lens (e.g. pseudoexfoliation syndrome)
15. A subject has a history of ocular trauma in their scheduled surgical eye
16. A subject that has undergone prior intraocular surgery in the scheduled surgical eye within the last 6 months or laser surgery within three months prior to screening
17. A subject with pupil abnormalities (non-reactive, tonic pupils, abnormally shaped pupils, or pupils that do not dilate at least 3.5 mm under mesopic/scotopic conditions) in their scheduled surgical eye.

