10.4.2 Analysis of the Primary Efficacy Endpoint(s)

The primary efficacy variable will be the severity of ocular pain report at visit 4, 5, 6 and 7 (post-op days 1, 3, 7 and 14). For analyses using the intent-to-treat (ITT) data set, all data from all subjects with at least one post-operative follow-up pain evaluation will be included. For the per protocol (PP) analyses dataset, data from subjects or visits with significant protocol deviations will be excluded.

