10.4.3 Analysis of the Secondary Endpoint(s)

The secondary efficacy variable will be the severity of ocular inflammation (anterior chamber cells and flare) report at visit 4, 5, 6 and 7 (post-op days 3, 7 and 14). For analyses using the intent-to-treat (ITT) data set, all data from all subjects with at least one post-operative follow-up inflammation evaluation will be included. For the per protocol (PP) analyses dataset, data from subjects or visits with significant protocol deviations will be excluded.

Efficacy analysis of primary and secondary endpoints will be based on observed data only. In the case of a significant amount of missing data, Last Observation Carried Forward may be used for sensitivity analysis.

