10.4.7 Planned Interim Analyses

An interim analysis will be performed to confirm that positive efficacy trends are being observed and that the enrolment should continue. The interim analysis will be performed after a minimum of 25 subjects have completed visit 7 in the study. The data will be unmasked and analysis of primary and secondary endpoints will be completed along with baseline descriptive statistics.

Sites will remain masked to treatment for the remainder of the study. A summary of the results may be shared with the sites but no individual site data will be generated or shared.

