10.4.8 Multiple Comparison/Multiplicity

N/A

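### The secondary inflammation endpoint is a responder measure in one section and a score in others, with Day 1 in or out and no rule for partial response; settle it before the unmasked interim

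*Combined protocol and SAP*

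**What the plan says.** Three places state the secondary endpoint.

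- Synopsis, Study Efficacy Variables: "Secondary: Mean anterior chamber scores for cells and flare at visits 4, 5, 6 and 7".
- Section 4.2.2: "complete (CR) and partial response (PR) to therapy regarding the Summed Ocular Inflammation Score (sum of the mean anterior chamber cells and flare"), compared with placebo at Days 3, 7 and 14.
- Section 10.4.3: severity of cells and flare, "report at visit 4, 5, 6 and 7 (post-op days 3, 7 and 14"). The matching sentence for pain in Section 10.4.2 has all four days: "report at visit 4, 5, 6 and 7 (post-op days 1, 3, 7 and 14"). The visit schedule gives "v4 = 1 day post-op".

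Complete response (CR) and partial response (PR) appear only in Section 4.2.2. Appendix 2 grades cells 0-4 and flare 0-4 but sets no response cut-off. Section 5.2 excludes "A subject with any signs of intraocular inflammation (cells/flare) in either eye at the screening visit". Section 10.4.3 names no test and relies on observed data, with last observation carried forward as an optional sensitivity analysis.

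On the interim, Section 10.4.7 says: "The data will be unmasked and analysis of primary and secondary endpoints will be completed along with baseline descriptive statistics". The section headed "10.4.8 Multiple Comparison/Multiplicity" is marked not applicable.

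**The concern.** A reader cannot tell whether the inflammation result is to be a comparison of scores or of responder proportions, or whether Day 1 counts. PR cannot be derived from anything in the documents. After at least 25 completers the data are unmasked, the secondary endpoint is analysed, and the result informs whether enrolment continues. If the definition is still open then, it can be settled by people who have seen the results, and more than one choice could later be presented as the planned one.

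Rescued eyes raise a linked question. Section 7.7.1 terminates a subject who needs a corticosteroid for any condition. Sections 7.9 and 7.9.1 allow corticosteroid rescue when stated criteria are met, and those criteria include cell or flare grade 3. Rescue therefore acts directly on this endpoint, yet no rule says how an eye rescued under the criteria is counted.

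**Working it through.** **1. The texts side by side**

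| Place | Measure | Day 1 |
|---|---|---|
| Synopsis | mean cell and flare scores | included (Visit 4) |
| 4.2.2 | CR and PR on the summed score | excluded |
| 10.4.3 | severity of cells and flare | in the visit list, not in the day list |

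The synopsis and 10.4.3 can be read as one score measure, with severity summarised as a mean. That leaves two real conflicts: responder against score, and Day 1 in or out.

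**2. Can CR and PR be derived?** The sum of the two grades runs from 0 to 4 + 4 = 8. CR has a natural reading, a sum of 0. PR has none:

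- A fall from screening is impossible. Eligible eyes have no cells or flare at screening, and a sum of 0 cannot fall.
- Day 1 is on treatment. The plug goes in 1-2 days before surgery, so Day 1 is 2-3 days after insertion.
- Plausible rules classify differently. Suppose one eye goes from 4 on Day 1 to 2 on Day 14, and another stays at 1. Under a 50% fall from Day 1, the first responds (2 = 0.5 × 4) and the second does not. Under a threshold of 1 or less, the reverse holds. An eye at 0 on Day 1 cannot fall and must be assigned by convention.

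**3. Sample sizes.** Section 10.5 makes no power calculation, so there is no plan figure to reproduce. From 75 subjects at 2:1: 75 × 2/3 = 50 and 75 × 1/3 = 25. At a 25-subject interim: 25 × 2/3 = 16.7, taken as 17 and 8.

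**4. No true effect, Day 14 only, two-sided 5% (Section 10.4.1).** Assumed model: Day 1 score = min(Poisson(μ), 8) with μ = 2, 3 or 4, thinned binomially to Days 3, 7 and 14 with three sets of keep rates between 0.4 and 0.9. That gives 9 settings of 40,000 trials each. Assumed tests: for the score, pooled t = (mean difference) / (s√(1/50 + 1/25)); for CR, Fisher exact.

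| Choice | 50/25 | 17/8 |
|---|---|---|
| Score alone | 4.8-5.0% | |
| CR alone | 3.2-4.1% | |
| Score or CR, free choice | 5.6-7.4% | 4.8-6.1% |
| Score, CR or one of three assumed PR rules | 6.3-10.5% | 4.8-8.7% |

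For score or CR, errors in the drug's favour are about 3.0-3.9% at 50/25 and 3.0-3.7% at 17/8, against 2.5% nominal. Repeat runs differ by a few tenths of a percentage point.

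**5. Effect as in the ILEVRO label (Appendix 5, Section 14).** Rates: 552/851 = 64.9% against 67/211 = 31.8%, and 331/540 = 61.3% against 63/268 = 23.5%. Fisher power is the sum of Bin(x; 50, p₁) × Bin(y; 25, p₂) over all tables with p ≤ 0.05. It comes to 76% and 88%. For the score, the probability of 0 was set to the label rate. Scores were either Poisson or zero-inflated, with the non-zero part 1 + Poisson(0.25 to 3), capped at 8.

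| | 64.9% v 31.8% | 61.3% v 23.5% |
|---|---|---|
| CR power, 50/25 | 76% | 88% |
| Score power, 50/25 | 62-92% | 72-98% |
| Exactly one of the two significant, 50/25 | 16-21% | 11-20% |
| Exactly one of the two significant, 17/8 | 15-27% | 18-33% |

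**The case against.** The best defence is that this is a pilot with no sample-size calculation, the endpoint is secondary, and the damage is limited. Much of that stands. Error inflation from choosing between score and CR is small, and smaller still in the drug's favour. Two correlated tests at these sample sizes will often disagree, so discordance alone does not show harm. There are also partial safeguards: Section 10.3 requires codes or classifications to be assigned before unmasking, and Section 10.6.3 requires each subject and visit to be assessed before the code is broken. But neither supplies a CR or PR rule to apply, and 10.6.3 does not clearly cover the interim.

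A reader might infer several stronger points that the documents do not support.

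- *Three incompatible endpoints.* The synopsis and 10.4.3 can be one score measure, and the day list in 10.4.3 matches 4.2.2.
- *The plan cannot be carried out.* Scores can be analysed and CR can be read as a sum of 0. Only PR cannot be computed.
- *Corticosteroid use is wholly unaddressed.* Section 7.9 treats use outside the rescue criteria as prohibited medication, and Section 10.1 allows exclusion for it. Section 7.7.1, like 7.9.1, follows subjects to Visit 7. The gap is criteria-based rescue.
- *A Day 1 reference is ruled out.* The absence of Day 1 from 4.2.2 would fit Day 1 as the reference. It would still be an on-treatment reference, and nothing says it was intended.
- *The repeated null in Section 10.2.* The secondary alternative copies the null. The pain hypotheses show what was meant, so this is a slip and adds no weight.

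**Conclusion.** The inconsistency is real and rests on the text alone: responder against score, Day 1 in or out, and no rule for PR. The main harm is that the definition can be fixed after unmasked data are seen; inflation of the error rate is secondary.

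The size is modest under no effect: about 5.6-7.4% two-sided at 50/25 and 4.8-6.1% at 17/8 for a free choice between score and CR at Day 14. It matters more if the drug works as the label suggests, when the choice changes significance in about 11-21% of trials at 50/25. These figures depend on assumed score models and tests. A different latent-normal model with uncorrected chi-square tests gave 10-11% for the best of mean, CR and PR at Day 14; there CR alone already ran at 5.8-6.6%.

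A reader might point to the 19-23% that the model in step 4 gives for free choice over definitions and days together. Most of that is multiplicity over days: the mean score at four days alone gives 10-14%. It should not be charged to the definition conflict. No figure is offered for rescue, because the documents give no rescue rates.

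**What to change.** Before any unmasked look:

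1. Put one per-subject definition, one day list and one named test in the synopsis, 4.2.2 and 10.4.3. One option among several is the proportion with cell grade + flare grade = 0 at a stated day, over a stated denominator, by two-sided Fisher exact test, with the summed score as supportive. The label's measure is resolution by the Day 14 visit over all randomized subjects. That is not the same as clearance at Day 14, so it should not be cited as the source unless both features are adopted.
2. Define PR by an explicit rule, or drop it.
3. Make the visit and day lists in 10.4.3 agree, and correct the secondary alternative in 10.2.
4. Reconcile Section 7.7.1 with 7.9 and 7.9.1 on criteria-based corticosteroid rescue; no view is taken here on which should stand. Then state how rescued or terminated eyes are counted. If they count as not resolved, add an observed-data sensitivity analysis and say that the endpoint has become a composite of clearing and not needing rescue.

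The cost is wording. No visit, subject or measurement is added: Section 11.1 already requires cell and flare values at each visit, and Section 7.9.1 puts rescue use on the Concomitant Medication CRF. The price is lost flexibility: days or measures not chosen become supportive, and PR may no longer be reported.
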